Statistical Methods	
The primary statistical analyses of PK data (Treatments “A” and “B” only) will be conducted on the population of subjects completing 28 days of dosing. Supporting evaluations will be performed for the cohort of subjects who received

	
at least one dose of study medication and provided any PK data.
 
Similarly, the primary statistical analyses of PD data (all Treatment groups) will be conducted on the population of subjects completing 28 days of dosing. Supporting evaluations will be performed for the cohort of subjects who received at least one dose of study medication and provided any PD data.
 
The safety analysis will be performed on all subjects who received at least one dose of study medication.
 
Incidence of subjects with suppressed E2 levels will be reported for each study period by treatment group. The incidence of subjects with suppressed E2 levels for the fourth treatment week (Day 22 and Day 29 combined) will be considered as a primary efficacy endpoint. The incidence of suppressed ovulation during the same period will also be reported. The FSH, LH, E2 and progesterone levels will be reported by treatment group for each evaluation period by using summary statistics. Changes in these parameters from prestudy baseline will also be summarized by treatment group.
 
The summaries will be provided for the PK parameters with a focus on steady-state concentration levels. PD and PK parameters will be graphed by treatment group for each evaluation period. Correlations between leuprolide concentration levels and PD parameters will be assessed.
 
Safety endpoints, study discontinuation information, changes in the physical and gynecological examination findings, and treatment-emergent changes in vital signs and clinical laboratory test results will be summarized. The subject incidence of TEAEs will be reported by the treatment received.
 
A detailed Statistical Analysis Plan will be developed prior to the database lock.

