#### **4. Changes from the Protocol**

Any changes in planned analyses compared to the protocol will be noted in this section.

Primary statistical analyses of the PD endpoints will utilize measurements for Treatment Day 22 and Treatment Day 29 (not Treatment Day 28 as noted in the protocol). This change will ensure consistent methodology across all treatment groups some of which (Treatments "C" and "D") did not have scheduled PD assessments on Treatment Day 28.

Suppression of  $E_2 \leq 50$  pg/mL,  $\leq 60$  pg/mL, and  $\leq 70$  pg/mL may also be assessed, if considered necessary.

The determination of the suppression of  $E_2$  or other PD endpoints across evaluation intervals was clarified.

An additional analysis for the adverse drug reactions (ADR) (excluding the PT “Menstrual Disorder”) was described.

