### 11.1 Pharmacodynamic Concentration and Parameters

A total of 11 PD blood samples for Treatments “A” and “B” and 10 PD blood samples for Treatment “C” will be taken for the determination of LH, FSH, E2, and progesterone levels. Serum concentrations of PD endpoints will be measured at screening and in the morning (in the Ovarest™ groups, just prior to oral dosing) on Dosing period Treatment Days 1, 8, 15, 22 and 28 (except for Treatment “C”), and in the morning of Evaluation Period Days 1 (or Day 29), 7, 14, 21 and 28.

A total of 10 PD blood samples for Treatment “D” will be taken for the determination of LH, FSH, E2, and progesterone levels. Serum concentrations of PD endpoints will be measured at screening and in the morning just prior to oral dosing) on Dosing period Treatment Days 1, 8, 15, 22, and in the morning of Evaluation Period Days 1 (or Day 29), 7, 14, 21 and 28.

The primary PD metric - suppression of E2 level - will be assessed at each on-treatment (28-day dosing) and 28-day post-dosing evaluation timepoint. Treatment dosing Day 22 and Treatment dosing Day 29 evaluations (separately and combined) will be considered as most important primary evaluations.

For the purposes of the statistical analyses, PD measurements for Day 29 will be considered as the last measurements of the 28-day dosing interval. This Day 29 measurement will NOT be included in the post-dosing PD evaluations. The post-dosing PD evaluations will utilize measurements collected on post-dosing days 7, 14, 21, and 28.

Suppression of E2 levels across various evaluation intervals (e.g., Days 22-29 of the dosing period, entire 28-day dosing period, and 28-day postdosing period) will be evaluated in two ways:

- (1) E2 level is considered suppressed during the evaluation period if a value below pre-specified threshold was reported **at least once** during that period. For example, if a subject had E2 ≤40 pg/mL at Day 29 and E2 > 40 pg/mL at Day 22, she will be categorized as a subject with a suppressed E2 level during the 22-29 Day evaluation period;
- (2) E2 level is considered suppressed during the evaluation period if a value below pre-specified threshold was reported **at each timepoint of that period**. For example, if a

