subject had  $E_2 \leq 40$  pg/mL at Day 29 and  $E_2 > 40$  pg/mL at Day 22, she will not be categorized as a subject with a suppressed  $E_2$  level during the 22-29 Day evaluation period; To be considered as a subject with a suppressed  $E_2$  level during that period,  $E_2$  must be  $\leq 40$  pg/mL on both Days 22 and 29.

The former definition, (1) will be considered as primary.

Note: For Treatments “A” and “B” additional protocol-specified evaluations will be performed for Days 22 and 28 of the dosing period

Similar approach will be utilized for other PD endpoints (e.g., a suppression of ovulation as evidence by progesterone level – see below).

In addition to a primary  $E_2$  suppression threshold ( $E_2 \leq 40$  pg/mL), a suppression of  $E_2 \leq 20$  pg/mL,  $\leq 50$  pg/mL,  $\leq 60$  pg/mL, and  $\leq 70$  pg/mL may also be assessed, if considered necessary. .

The suppression of ovulation (as evidenced by progesterone levels  $< 3$  ng/mL) will be assessed at each on-treatment (28-day dosing) and 28-day post-dosing evaluation timepoint. Treatment dosing Day 22 and Treatment dosing Day 28 (Day 29 for Treatments “C” and “D”) evaluations (separately and combined) will be considered as most important (primary) evaluations.

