## 11.2 Statistical Analyses

Individual and mean concentration of hormonal levels versus nominal time curves will be presented by treatment group for each evaluation timepoint. Descriptive statistics (sample size “n”, mean, standard deviation, coefficient of variation, median, minimum value and maximum value) of hormonal levels will be presented for each timepoint.

Summaries of the LH, FSH,  $E_2$ , and progesterone levels will be reported for each dosing and post-dosing evaluation timepoint, for the dosing days 22 and 28 (Day 29 for Treatments “C” and “D”) (combined: i.e. the maximum among the 2 values) and, optionally, for the entire 28-day dosing period and the entire post-dosing Evaluation Period. Changes from pre-dosing baseline in LH, FSH,  $E_2$  and progesterone levels will also be summarized (sample size “n”, mean, standard deviation, median, minimum value and maximum value) at each on-treatment evaluation timepoint. Pre-dosing baseline for all PD metrics is the highest value across two observations: (a) screening measurement and (b) measurement taken just prior to the first dose of the study drug. Similar summaries will be provided for the follow-up visits (postdosing Days 7, 14, 21, and 28). In addition, time to return to pre-study baseline hormonal levels could be estimated.

Summaries of PD metrics may be further stratified by the cycle period (days) of the start of dosing. Categorical variables will be summarized by using frequency counts and percentages for each treatment by visits involved. In addition, the number of patients with missing values will be displayed.

Additionally, correlations between leuprolide concentration levels and PD parameters will be examined graphically. PD parameters may include LS, FSH, E2 and progesterone levels. These evaluations will not be performed for Treatment “D”.

Number of vaginal (menstrual) bleeding days will be summarized by treatment group for 28 days of therapy and for 28 days of post-study follow-up. The subject incidence of the onset of menstrual period after completion of therapy will be reported for each treatment group.

The onset of menstrual period is defined as at least three consecutive bleeding/spotting days during the 28-day postdosing period.

Additional PD analyses could be performed if necessary.

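### SAP 11.1 makes Days 22/28 primary for ovulation suppression in arms A and B but Days 22/29 in C and D, against SAP Section 4 and the protocol, which point to Days 22/29 in every arm

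*SAP*

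**What the plan says.** SAP Section 4 declares a change from the protocol: "Primary statistical analyses of the PD endpoints will utilize measurements for Treatment Day 22 and Treatment Day 29", expressly in place of Day 28. The reason given is "This change will ensure consistent methodology across all treatment groups", because C and D have no Day 28 PD sample. The rule covers the PD endpoints in the plural and exempts no endpoint or arm.

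SAP 11.1 applies this to E2 suppression in all arms: "Treatment dosing Day 22 and Treatment dosing Day 29 evaluations (separately and combined) will be considered as most important primary evaluations". It adds that "PD measurements for Day 29 will be considered as the last measurements of the 28-day dosing interval". For A and B it notes that "additional protocol-specified evaluations will be performed for Days 22 and 28 of the dosing period", and it says other PD endpoints, with ovulation suppression as the example, follow a similar approach.

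In its last paragraph, SAP 11.1 labels as primary for ovulation suppression "Treatment dosing Day 22 and Treatment dosing Day 28 (Day 29 for Treatments" C and D). SAP 11.2 uses the same split for the combined LH, FSH, E2 and progesterone summaries, "for the dosing days 22 and 28 (Day 29 for Treatments" C and D), taking the larger of the two values.

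In the protocol, both the synopsis (Pharmacodynamic Parameters) and Section 12.3 make Day 22 and Postdosing Day 1 primary for ovulation, with no distinction by arm. Section 7.1 equates Postdosing Day 1 with Treatment Day 29. The synopsis (Statistical Methods) sets the E2 endpoint on Days 22 and 29 combined and continues: "The incidence of suppressed ovulation during the same period will also be reported".

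**The concern.** A result labelled primary would rest on different days in different arms, which is what Section 4 says it removes. A programmer working from the ovulation paragraph of SAP 11.1 and one working from Section 4 or the protocol would produce different primary ovulation tables for A and B.

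The split also separates the oral arms. Comparing PD across 4 mg qd, 4 mg bid and 10 mg bid is a primary objective. Under Protocol 7.2 the A/B Day 28 sample is drawn before that day's first dose, so it follows 27 days of dosing, whereas the Day 29 sample in D follows 28.

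**Working it through.** The plan gives no figure to reproduce. The check compares the passages and counts scheduled draws.

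**Days named as primary or most important**

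| Source | Endpoint | A and B | C and D |
|---|---|---|---|
| Protocol synopsis (PD Parameters) and 12.3 | E2 | 22, 28 | 22, 28 |
| Protocol synopsis (PD Parameters) and 12.3 | Ovulation | 22, 29 | 22, 29 |
| SAP Section 4 | PD endpoints | 22, 29 | 22, 29 |
| SAP 11.1 | E2 | 22, 29 | 22, 29 |
| SAP 11.1 | Ovulation | 22, 28 | 22, 29 |

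The protocol's Day 28 wording concerns E2 only, and that is the text Section 4 replaces. Day 28 for ovulation in A/B is therefore not carried over from the protocol. It is a new departure that Section 4 does not record.

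**Is Day 29 available in every arm?** Draws from Protocol Appendix B (footnote m) and SAP 11.1:
- A and B: screening; Days 1, 8, 15, 22, 28, 29; postdosing Days 7, 14, 21, 28. That is 1 + 6 + 4 = 11, as stated.
- C and D: the same without Day 28, 1 + 5 + 4 = 10, as stated.

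Day 29 is scheduled in all four arms and Day 28 only in A and B, so Days 22/29 can be used everywhere.

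**Subjects affected.** Protocol 7.1 gives 9 enrolled in each of A and B: 9 + 9 = 18. One of the 23 initial subjects was withdrawn, arm not stated, which leaves 17 or 18 in A and B.

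**Single-day rate.** One subject whose progesterone lies on different sides of 3 ng/mL on Days 28 and 29 shifts her arm's rate by 1/9 = 11.1 points, or 1/8 = 12.5 points if 8 are analysed.

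**Combined result.** SAP 11.1 has two rules: suppressed at least once in the period (primary) and suppressed at every timepoint. If Days 28 and 29 disagree:

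| Day 22 | At least once: 22/28 v 22/29 | Every timepoint: 22/28 v 22/29 |
|---|---|---|
| Suppressed | same | differ |
| Not suppressed | differ | same |

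Under the primary rule the combined result therefore changes only when Day 22 was not suppressed and Days 28 and 29 disagree.

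**Combined summaries in SAP 11.2.** For E2, being at or below 40 pg/mL on both days is the same as the maximum of the two being at or below 40. SAP 11.1 applies the two-day rule on Days 22/29, while SAP 11.2 takes the maximum over Days 22/28 in A/B. In those arms the two E2 outputs need not agree.

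**Whole dosing period.** After the first dose and up to Day 29, A/B have five draws (8, 15, 22, 28, 29) and C/D have four (8, 15, 22, 29). An extra draw can only raise, or leave unchanged, an at-least-once rate and only lower, or leave unchanged, an every-timepoint rate.

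**The case against.** The strongest counter-argument is that SAP 11.1 already points the right way. It calls Days 22/28 in A/B additional, says ovulation follows the E2 approach, and assesses ovulation at every timepoint, so the A/B Day 29 rates will be reported. On that view only a label is at issue. The reporting point stands and limits the harm. The rest does not remove the conflict: the ovulation paragraph attaches the primary label to Day 28, so the section contradicts itself as well as Section 4.

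The practical effect is also said to be small, and this stands. E2 is the primary PD metric, no inferential analysis is planned, and the days differ by one. The predose Day 28 sample falls at the same nominal interval after the previous dose as the Day 29 sample (24 hours in A, 12 hours in B).

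Three points of scope also stand:
- The denominators 8 and 9 are illustrative, because the primary PD population also excludes major protocol violators, whose number is not given.
- The draw count shows what was scheduled, not what was obtained. One subject was withdrawn on post-dose Day 1; if that means Day 29, she could have a Day 28 value but no Day 29 value.
- The SAP 11.2 summaries and the whole-period results are not labelled primary, so neither strictly contradicts Section 4. The table shells are a separate document and may already settle the days, though they would not correct the SAP text.

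**Conclusion.** The concern holds. For ovulation suppression, SAP 11.1 contradicts SAP Section 4, the protocol, and its own statement that Days 22/28 are additional in A/B. The departure from the protocol is undeclared, and the sampling schedule gives no reason for it.

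The affected output is the primary-labelled ovulation result in A and B (18 enrolled), plus the combined hormone summaries, which do not fit the aim of a consistent method. The primary E2 suppression endpoint is untouched. The numerical effect cannot be computed, because the documents do not say how many subjects cross 3 ng/mL between Days 28 and 29. The text should be corrected, but the conflict does not threaten the study's main conclusion.

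**What to change.** 1. SAP 11.1, ovulation paragraph: make Days 22 and 29, separately and combined, primary for all four arms.
2. SAP 11.2: use Days 22 and 29 for the combined hormone summaries in all four arms, so that they match the suppression tables.
3. Keep Days 22/28 in A and B only as the additional evaluation that SAP 11.1 already describes.
4. Optional, and beyond the contradiction itself: where whole-dosing-period results are shown side by side, use the visits common to all arms (8, 15, 22, 29).

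The cost is two short SAP edits, a third if item 4 is adopted, and the matching table shells. No new samples are needed. Item 4 leaves the A/B Day 28 value out of the side-by-side whole-period summary, but it remains in the per-visit and additional A/B summaries.

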**Methodology and Evaluations**

Depot. Newly enrolled subjects will receive the third Ovarest dose (Treatment “D”) that will be administered in the same fashion as Treatment “B”. Assessments of the PD profile of treatment “D” will also mimic evaluations of Treatment “B”. However, unlike other Ovarest groups, Treatment “D” will not have comprehensive assessments of the PK profile. The subjects that have already participated in this study may be invited to receive Treatment “D” if they are eligible per the study inclusion and exclusion criteria. The subjects in Treatments “A”, “B”, and “C” will start dosing (Treatment Day 1) on either Day 1 up to Day 4 of their menstrual cycle, or within the last 11 days of their menstrual cycle. (Note: onset of menstrual period is considered as day 1 of the menstrual cycle.) Please see Appendix G for a table of acceptable days for initiation of dosing in relation to cycle length. Permissible time windows for the start of the dosing will be determined based on the onset of menstrual period prior to the screening visit or a projected start of the next menstrual cycle. The projected start of the next menstrual cycle will be based on the date of onset of menses during the screening period and the typical length of the normal menstrual cycle for each subject as reported by each subject during the screening visit. Subjects enrolled to the third oral dose (Treatment “D”) will have a dosing initiation visit scheduled 5-9 days before the anticipated start of their next menstrual cycle, based on their self-reported menstrual cycle length and the day the current menstrual cycle began. The 4-mg qd oral dose will be administered once daily, in the morning, on an empty stomach; the 4-mg and 10-mg bid oral doses will be administered twice daily, in the morning and in the evening, 12 hours apart and on an empty stomach. Note: On an empty stomach means that the oral doses are administered at least 2 hours before or at least 2 hours after the meal. Oral administration instructions are applicable to both on-site and at-home dosing. For at-home dosing, each subject will take the oral dose with approximately 240 mL of water. Subjects randomized to the two oral doses (Treatments “A” and “B”) will have twenty-four (24) serial serum samples drawn on Treatment Days 1 and 28 immediately prior to dosing (0 time), and at 0.5, 1, 1.5, 2, 2.5, 3, 3.5, 4, 4.5, 5, 6, 7, 8, 10, 12, 13, 14, 15, 16, 17, 18, 20, and 24 hours following oral dosing. For the IM injection (Treatment “C”), serial serum samples will also be drawn on Treatment Day 1, prior to dosing (0 time), at 0.5, 1, 2, 6, 12, 18, and 24 hours postdosing. Blood samples for the IM injection will also be taken in the morning on Day 29. Additional blood samples for all subjects will be taken in the morning (in the oral groups, just prior to dosing) on Treatment Days 8, 15, and 22. Samples will be appropriately stored until they can be assayed for leuprolide and hormonal levels. Serum concentrations of luteinizing hormone (LH) and follicle-stimulating hormone (FSH), and plasma concentrations of E2 and progesterone will be measured (immediately prior to dosing) on Treatment Days 1, 8, 15, 22, and in the morning of Day 29.

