### 12.3 Pharmacodynamic Parameters and Analyses

As noted earlier, PD assessments (LH, FSH, E2, and progesterone) will be performed during the Screening Visit and immediately prior to dosing on Treatment Days 1, 8, 15, 22, and 29. Additional PD assessments will be performed during the follow-up visits (postdosing Days 7, 14, 21 and 28).

The primary PD metric - suppression of E2 level - will be assessed at each on-treatment evaluation timepoint. Treatment Day 22 and Treatment Day 28 evaluations (separately and combined) will be considered as most important. The summaries will also be provided across the entire dosing period and the entire postdosing period, separately and combined. The summaries of PD metrics may be further stratified by the cycle period (days) of the start of dosing.

In addition to a primary E2 suppression threshold (E2 ≤40 pg/mL), a suppression of E2 below 20 pg/mL may also be assessed, if considered necessary. The suppression of ovulation (as evidenced by progesterone levels <3 ng/mL) will be evaluated with Treatment Day 22 and Postdosing Day 1 assessments positioned as primary. Changes from predosing baseline in E2 and progesterone levels will also be summarized at each on-treatment evaluation timepoint. Predosing baseline for all PD metrics is the highest value across two observations: (a) screening measurement and (b) measurement taken just prior to the first dose of the study drug. Similar summaries will be provided for the follow-up visits (postdosing Days 7, 14, 21, and 28). In addition, time to return to prestudy baseline hormonal levels could be estimated.

PD parameters will be graphed by treatment group for each evaluation period.

Additionally, correlations between leuprolide concentration levels and PD parameters will be examined.

Number of vaginal (menstrual) bleeding days will be summarized by treatment group for 28 days of therapy and for 28 days of poststudy follow-up. The subject incidence of the onset of menstrual period after completion of therapy will be reported for each treatment group.

Further details of the PD data analysis will be disclosed in the SAP.

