**Table 3-1 Treatment Description**

Treatment	Description
A	Leuprolide Oral Tablet, Ovarest™ 4 mg, administered qd for 28 consecutive days
B	Leuprolide Oral Tablet, Ovarest™ 4 mg, administered bid for 28 consecutive days
C	Leuprolide Acetate IM, Lupron Depot® 3.75 mg, administered for one month of therapy
D	Leuprolide Oral Tablet, Ovarest™ 10 mg, administered bid for 28 consecutive days

Subjects meeting the eligibility criteria were to be initially randomized to receive one of the two doses of Ovarest™ for 28 days or a monthly IM dose of Lupron Depot®. After the protocol amendment, subjects meeting the eligibility criteria were to be enrolled in Treatment “D” The initially randomized subjects had to start dosing (Treatment Day 1) on either days 1-4 or days 18-28 of their menstrual cycle. Subjects enrolled to the third oral dose (Treatment “D”) had to start dosing 5-9 days before the anticipated start of their next menstrual cycle, based on their self-reported menstrual cycle length and the day the current menstrual cycle began.

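### SAP 11.1 makes single-day progesterone below 3 ng/mL primary evidence of suppressed ovulation, but the dosing-start windows can put the sampling day outside the luteal phase, most clearly Day 22 in Treatment D

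*SAP*

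**What the plan says.** Protocol 12.3 sets the criterion: "The suppression of ovulation (as evidenced by progesterone levels <3 ng/mL) will be evaluated". It adds that this "will be evaluated with Treatment Day 22 and Postdosing Day 1 assessments positioned as primary". Postdosing Day 1 is Treatment Day 29.

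SAP 11.1 keeps the threshold but names Day 22 with Day 28 in A and B, and Day 22 with Day 29 in C and D. These "evaluations (separately and combined) will be considered as most important (primary) evaluations". Each single-day rate is therefore primary in its own right.

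For combining days, SAP 11.1 gives two definitions for estradiol: (1) below threshold at least once, and (2) below threshold at every timepoint. It then states: "The former definition, (1) will be considered as primary". The same approach is carried over to progesterone.

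The start windows are also fixed. Per the protocol synopsis, women in A, B and C start "on either Day 1 up to Day 4 of their menstrual cycle, or within the last 11 days of their menstrual cycle". SAP 3.3 says that women in D "had to start dosing 5-9 days before the anticipated start of their next menstrual cycle". Eligible cycle length is 21 to 35 days (Protocol 8.1). Stratifying the PD summaries by start day is optional (Protocol 12.3, SAP 11.2).

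**The concern.** Progesterone is low in every ovulating woman before ovulation and around menses. A value below 3 ng/mL shows absent ovulation only if the sample falls where a luteal rise would otherwise be seen. Here the start window largely decides where it falls, so on a badly placed day a woman can meet the criterion with no drug effect.

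Treatment D is the arm most exposed. It was added after both 4 mg regimens fell well short of Lupron Depot on estradiol. It is non-randomised, has at most 12 women and is reported descriptively, so the observed percentages are the result. A Day 22 rate that inert tablets would also produce is not evidence that the 10 mg regimen works. The no-drug rate on Day 22 also differs between D and A-C, so timing alone can create a difference between arms.

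**Working it through.** The documents give no false-pass rate to reproduce. The check asks what share of women with unaltered ovulatory cycles would meet the criterion.

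**Inputs from the documents:** the threshold and days above; start windows from Appendix G (A-C: cycle days 1-4, or days L-10 to L of an L-day cycle; D: 5-9 days before menses); L from 21 to 35. Protocol 7.1 and SAP 3.3 give cycle days 18-28 as the late window for A-C, which matches Appendix G only at L = 28.

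**Assumptions, not in the documents:** a 14-day luteal phase, start days spread evenly over the allowed window, each L weighted equally, and progesterone at or above 3 ng/mL from cycle day L-14+a to cycle day L-b. The pair (a, b) runs from (1, 1), the widest high window, to (4, 3), the narrowest.

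**Treatment D.** A woman who starts k days before menses (k = 5 to 9) has menses on Treatment Day k+1, so Treatment Day d is cycle day d-k.
- Day 22: 22-5 = 17 down to 22-9 = 13, for every L from 21 to 35.
- Day 29: 24 down to 20, for L of 24 or more.
- At L = 28 the high window is days 15-27 (widest) to 18-25 (narrowest). Of cycle days 13-17, two of five (40%) to five of five (100%) lie outside it. With (a, b) = (3, 2) the window is 17-26 and four of five (80%) pass. Cycle days 20-24 always lie inside, so Day 29 passes 0%.

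**A-C.** A start on cycle day s puts Treatment Day t on cycle day ((s+t-2) mod L)+1. At L = 28:
- Early starters (s = 1-4): Day 22 is cycle day 22-25, so 0% pass. Day 28 is cycle day 28, 1, 2 or 3, and Day 29 is cycle day 1-4, so 100% pass either. If the last cycle day still counted as high, the Day 28 figure would be three of four (75%).
- All 15 start days: Day 22 passes 4/15 to 7/15 (27-47%), Day 28 passes 4/15 to 7/15 (27-47%), and Day 29 passes 5/15 to 7/15 (33-47%).

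**Combining under definition (1)** does not help. At L = 28 no A-C start passes both Day 22 and Day 29, so at least one is passed by (4+5)/15 = 60% to (7+7)/15 = 93%. In D the figure stays at 40-100%.

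Enumerating all start days and cycle lengths gives these no-drug pass rates:

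| Rule | L = 28 | L = 26-32 | L = 21-35 |
|---|---|---|---|
| D, Day 22 alone | 40-100% | 57-91% | 47-67% |
| D, Day 29 alone | 0% | 0-11% | 17-47% |
| D, Days 22 and 29 both | 0% | 0-9% | 4-20% |
| A-C, Days 22 and 29 both | 0% | 1-12% | 8-24% |

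Adding Day 15 to the both-days rule leaves D unchanged and lowers A-C over 21-35 days from 8-24% to 4-12%.

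**The case against.** The case against acting has several sound parts. The primary efficacy endpoint is estradiol suppression in the fourth treatment week, and the protocol synopsis says only that suppressed ovulation will also be reported. No inferential analysis is planned. Progesterone is measured at every weekly visit, individual curves will be shown, and the both-days rule is already in the SAP as definition (2). SAP 11.2 also summarises the combined hormone level as the higher of the two days. All the percentages rest on luteal timing from outside the documents, and an active drug may shift the cycle, so the untreated woman is a benchmark and not a prediction.

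A reader might also infer more than the documents support:
- **That most untreated women would pass either day in every arm.** Across all A-C starts at a 28-day cycle each single day passes 27-47%. A majority appears for Day 22 in D under most of the assumed windows, and for early A-C starters on the last day.
- **That inert tablets in D would be reported as a primary success.** Day 29 in D is equally primary and well placed for cycles of 26-32 days. A high Day 22 rate would then stand beside a Day 29 rate near zero.
- **That Day 15 has to join the primary rule.** In D it changes nothing.

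These points limit the stakes. They do not remove the defect: the single-day rates remain primary, definition (2) does not, and stratification by start day is not required.

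**Conclusion.** The point holds in a limited form. The plan gives primary standing to single-day rates whose meaning depends on cycle phase, and it does not tie the days to phase. The clearest failure is Day 22 in D, where cycle day 13-17 follows from the start window alone. The size of the false-pass rate needs the assumed luteal timing: 40-100% at 28 days, 57-91% over 26-32 days and 47-67% over 21-35 days. Day 29 in D is sound for mid-length cycles but less so over the full eligible range (17-47%). In A-C the problem depends on the start day: early starters at a 28-day cycle are well placed on Day 22 and badly placed on the last day. The both-days rule removes most of the false passes but not those at the extremes of cycle length.

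**What to change.** In SAP 11.1:
1. Remove 'separately' from the primary ovulation evaluations.
2. Make definition (2) the primary ovulation result: progesterone below 3 ng/mL on both Day 22 and the last on-treatment day.
3. Use the same last day, Day 29, in all arms. SAP section 4 and Protocol 12.3 already do so; the Day 28 wording for A and B in SAP 11.1 and 11.2 should be reconciled with them.
4. Keep the single-day rates as descriptive results, shown with each woman's projected cycle day from her recorded menses dates and reported cycle length.
5. Report the rule with Day 15 added as a sensitivity result only. Day 15 lies outside the fourth-week target, and the label in Appendix D describes initial stimulation before suppression.

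All samples are already scheduled, so the cost is SAP wording and one derived variable. The ovulation-suppression rates will look less favourable. Because SAP section 13 imputes nothing, the text should also say how a woman with only one of the two samples is counted.
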